### 7.3.6.4 Functional Assessment of Chronic Illness Therapy-Fatigue

The FACIT-Fatigue is a 13-item questionnaire that assesses self-reported fatigue and its impact upon daily activities and function (Wolfe 1996). It uses a 5-point Likert-type scale (0 = not at all; 1 = a little bit; 2 = somewhat; 3 = quite a bit; 4 = very much). As each of the 13 items of the FACIT-Fatigue scale ranges from 0–4, the range of possible scores is 0-52, with 0 being the worst possible score and 52 the best. To obtain the 0-52 score, each negatively worded item response is recoded so that 0 is a bad response and 4 is good response. All responses are added with equal weight to obtain the total score. Fatigue is among the most prevalent symptoms of SLE, and can have profound effects on subjects' HRQoL (Wolfe 1996, Yellen 1997). The FACIT-Fatigue has been validated in subjects with SLE being a valid and responsive measure of fatigue in subjects with SLE (Hewlett 2005, Kosinski 2013, Lai 2011, Strand 2015).

### 7.3.6.5 EuroQoL 5 Dimension 5 Levels

The EQ-5D-5L questionnaire is a generic measure of health status that provides a simple descriptive profile and a single index value (Aggarwal 2009).

The EQ-5D-5L profile defines health in terms of mobility, self-care, usual activities, pain or discomfort, and anxiety or depression. Each dimension has five levels: no problems, slight problems, moderate problems, severe problems, and extreme problems. The digits for five dimensions can be combined in a five-digit number describing the respondent's health state.

EQ-5D-5L health states, defined by the EQ-5D-5L descriptive system, may be converted into a single index value. The index values, presented in country specific value sets, facilitate the calculation of quality-adjusted life years that are used to inform economic evaluations of health care interventions.

The EuroQoL VAS records the respondent's self-rated health on a 20 cm vertical, visual analogue scale with endpoints labelled 'the best health you can imagine' and 'the worst health you can imagine'. This information can be used as a quantitative measure of health as judged by the individual respondents.

Higher scores on both EQ-5D-5L scales represent a better QoL.

## 7.4 Assessment of Safety

The safety profile of the IMP will be assessed through the recording, reporting and analysis of Baseline medical conditions; AEs; physical examination findings including vital signs, ECGs, and laboratory tests (including Ig as detailed Section 7.3.6 and B cell counts).

Comprehensive assessment of any apparent toxicity experienced by each subject will be performed from the time of giving informed consent and throughout the study. The Investigator will report any AEs, whether observed by the Investigator or reported by the subject (see Section 7.4.1.2). The Reporting Period for AEs is described in Section 7.4.1.3.

### 7.4.1 Adverse Events

#### 7.4.1.1 Adverse Event Definitions

##### Adverse Event

An AE is any untoward medical occurrence in a subject or clinical investigation subject administered a pharmaceutical product, regardless of causal relationship with this treatment. An AE can therefore be any unfavorable and unintended sign (including an abnormal laboratory finding), symptom, or disease temporally associated with the use of a medicinal product, whether or not considered related to the medicinal product.

For surgical or diagnostic procedures, the condition/illness leading to such a procedure is considered as the AE rather than the procedure itself.

The Investigator is required to grade the severity or toxicity of each AE.

Investigators will reference the National Cancer Institute - Common Terminology Criteria for AEs (NCI-CTCAE), version 4.03 CTCAE 2010, a descriptive terminology that can be used for AE reporting.

A general grading (severity/intensity; hereafter referred to as severity) scale is provided at the beginning of the above referenced document, and specific event grades are also provided.

Only if a particular AE's severity is not specifically graded by the guidance document, the Investigator is to use the general NCI-CTCAE definitions of Grade 1 through Grade 5 following his or her best medical judgment.

The five general grades are:

- Grade 1 or Mild
- Grade 2 or Moderate
- Grade 3 or Severe
- Grade 4 or Life-threatening

- Grade 5 or Death.

According to Sponsor convention, any clinical AE with severity of Grade 4 or 5 must also be reported as an SAE. However, a laboratory abnormality of Grade 4, such as anemia or neutropenia, is considered serious only if the condition meets one of the serious criteria described below.

If death occurs, the primary cause of death or event leading to death should be recorded and reported as an SAE. “Fatal” will be recorded as the outcome of this specific event and death will not be recorded as a separate event. Only, if no cause of death can be reported (e.g., sudden death, unexplained death), the death per se might then be reported as an SAE.

Investigators must also systematically assess the causal relationship of AEs to IMP(s)/study treatment (including any other non-IMPs, etc.) using the following definitions. Decisive factors for the assessment of causal relationship of an AE to the IMP include, but may not be limited to, temporal relationship between the AE and the IMP, known side effects of IMP, medical history, concomitant medication, course of the underlying disease, study procedures.

**Unrelated:** Not reasonably related to the IMP/study treatment. AE could not medically (pharmacologically/clinically) be attributed to the IMP/study treatment under study in this CTP. A reasonable alternative explanation must be available.

**Related:** Reasonably related to the IMP/study treatment. AE could medically (pharmacologically/clinically) be attributed to the IMP/study treatment under study in this CTP.

### **Abnormal Laboratory Findings and Other Abnormal Investigational Findings**

Abnormal laboratory findings and other abnormal investigational findings (e.g., on an ECG trace) should not be reported as AEs unless they are associated with clinical signs and symptoms, lead to treatment discontinuation or are considered otherwise medically important by the Investigator. If a laboratory abnormality fulfills these criteria, the identified medical condition (e.g., anemia, increased ALT) must be reported as the AE rather than the abnormal value itself.

### **Serious Adverse Events**

An SAE is any untoward medical occurrence that at any dose:

- Results in death.
- Is life-threatening. (Note: The term “life-threatening” refers to an event in which the subject is at risk of death at the time of the event, not an event that hypothetically might have caused death if it was more severe)
- Requires inpatient hospitalization or prolongs an existing hospitalization, except in the case of hospitalizations due to protocol-defined SLE flares.
- Results in persistent or significant disability or incapacity.
- Is a congenital anomaly or birth defect.

- Is otherwise considered to be medically important. (Note: Important medical events that may not result in death, be life-threatening, or require hospitalization may be considered as SAEs when, based upon appropriate medical judgment, they may jeopardize the subject or may require medical or surgical intervention to prevent one of the outcomes listed above. Examples of such events include allergic bronchospasm requiring intensive treatment in an emergency room or at home, blood dyscrasias or convulsions that do not result in inpatient hospitalization, or the development of drug dependency or drug abuse.)

For the purposes of reporting, any suspected transmission of an infectious agent via an IMP is also considered an SAE, as described in 7.4.1.4.

#### **Events that Do Not Meet the Definition of an SAE**

Elective hospitalizations to administer, or to simplify study treatment or study procedures (e.g., an overnight stay to facilitate intravenous therapy) are not considered SAEs. However, all events leading to unplanned hospitalizations or unplanned prolongation of an elective hospitalization (e.g., undesirable effects of any administered treatment) must be documented and reported as SAEs, except for unplanned hospitalizations due to flare of SLE.

#### **Events Not to Be Considered as AEs/SAEs**

Medical conditions present at the initial study visit that do not worsen in severity or frequency during the study are defined as Baseline Medical Conditions and are not to be considered AEs.

Worsening of the underlying disease is not routinely to be considered an AE or SAE, but is rather an efficacy endpoint, unless deemed to be causally related to the IMP.

However, if significant adverse signs or symptoms occur in association with complications or a prolonging of a hospitalization originally due to SLE flare, then these specific complications or hospital prolongation events should be recorded as AEs.

#### **Exacerbation of SLE**

SLE flares would not usually be reported as AEs unless they are unexpected in the context of the subject's medical history. Further, the AE report should describe the event, rather than reporting an AE of "SLE flare" unless it is unavoidable. SAEs due to SLE flare are always reported, whether or not it is consistent with the subjects' prior history. As for AE reports, the SAE report should describe the events, and avoid reporting an SAE of "SLE flare".

### **7.4.1.2 Methods of Recording and Assessing Adverse Events**

At each study visit, the subject will be asked about changes in his/her condition. During the Reporting Period of the study, any unfavorable changes in the subject's condition will be recorded as AEs, whether reported by the subject or observed by the Investigator, unless it is a lupus flare that is not unexpected based on the subject's medical history.

Complete, accurate and consistent data on all AEs experienced for the duration of the Reporting Period (defined below) will be reported on an ongoing basis in the appropriate section of the eCRF. All SAEs must be additionally documented and reported using an SAE Report Form as described in Section 7.4.1.4.

It is important that each AE report include a description of the event, its duration (onset and resolution dates [and times to be completed when relevant and possible to assess the time of AE onset relative to treatment administration]), its severity, its relationship with the study treatment, any other potential causal factors, any treatment given or other action taken (including dose modification or discontinuation of the IMP) and its outcome. In addition, SAEs should be identified and the appropriate seriousness criteria documented.

Specific guidance can be found in the eCRF Completion and Monitoring Conventions provided by the Sponsor or designee.

### **7.4.1.3 Definition of the Adverse Event Reporting Period**

The AE Reporting Period for safety surveillance begins when the subject is screened (date of first signature of informed consent) and continues through the study's Post Treatment Follow-Up Period, defined as the Safety Follow-Up Period (EOT through Follow-Up Week 4). SAEs occurring after a subject has taken the last dose of IMP will be collected throughout the subject's participation until the end of the Safety Follow-Up Period, regardless of the Investigator's opinion of causation. Thereafter, SAEs are not required to be reported unless the Investigator determines the SAE was related to IMP, or protocol procedure.

Any SAE assessed as related to M2951 must be reported whenever it occurs, irrespective of the time elapsed since the last administration of M2951.

### **7.4.1.4 Procedure for Reporting Serious Adverse Events**

#### **Serious Adverse Events**

In the event of any new SAE occurring during the Reporting Period, the Investigator must immediately (i.e., within a maximum of 24 HOURS after becoming aware of the event) inform the Sponsor or its designee by completing the SAE Report form in the eCRF following specific completion instructions.

In exceptional circumstances, an SAE (or follow-up information) may be reported by telephone; in these cases, an SAE Report Form must be completed immediately thereafter.

Relevant pages from the eCRF may be provided in parallel (e.g., medical history, concomitant drugs). Additional documents may also be provided by the Investigator, if available (e.g., laboratory results, hospital report, autopsy report). In all cases, the information provided in the SAE Report Form (clinical trial) must be consistent with the data on the event that are recorded in the corresponding sections of the eCRF.

The Investigator/reporter must respond to any request for follow-up information (e.g., additional information, outcome and final evaluation, specific records where needed) or to any question the Sponsor/designee may have on the AE within the same timelines as described for initial reports. This is necessary to permit a prompt assessment of the event by the Sponsor or designee and (as applicable) to allow the Sponsor to meet strict regulatory timelines associated with expedited safety reporting obligations.

Requests for follow-up will usually be made via the responsible Monitor, although in exceptional circumstances the Global Drug Safety department may contact the Investigator directly to obtain further information or to discuss the event.

#### **7.4.1.5 Safety Reporting to Health Authorities, Independent Ethics Committees/ Institutional Review Boards and Investigators**

The Sponsor or designee will send safety notifications to Health Authorities in accordance with applicable laws and regulations.

The Investigator must comply with any applicable site-specific requirements related to the reporting of SAEs (and in particular, deaths) involving study subjects to the IEC/IRB that approved the study.

In accordance with ICH GCP, the Sponsor/designee will inform the Investigator of “findings that could adversely affect the safety of subjects, impact the conduct of the study or alter the IEC’s/IRB’s approval/favorable opinion to continue the study.” In particular and in line with respective regulations, the Sponsor/designee will inform the Investigator of AEs that are both serious and unexpected and are considered to be related to the administered product (SUSARs). The Investigator should place copies of safety reports in the Investigator Site File. National regulations with regard to safety report notifications to Investigators will be taken into account.

For Japan only - In accordance with ICH GCP and the Japanese ministerial ordinance on GCP, the Sponsor/designee will inform the Investigator and the head of the study site of “findings that could adversely affect the safety of subjects, impact the conduct of the study or alter the IEC’s/IRB’s approval/favorable opinion to continue the study.” In particular and in line with respective regulations, the Sponsor/designee will inform the Investigator and the head of the study sites of AEs that are both serious and unexpected and are considered to be related to the administered product (SUSARs). The Investigator should place copies of safety reports in the Investigator Site File. National regulations with regard to safety report notifications to Investigators will be taken into account. The head of the study site should also maintain copies of safety reports appropriately.

When specifically required by regulations and guidelines, the Sponsor/designee will provide appropriate Safety Reports directly to the concerned lead IEC/IRB and will maintain records of these notifications. When direct reporting is not clearly defined by national or site-specific regulations, the Investigator will be responsible for notifying the applicable IEC/IRB of any safety reports provided by the Sponsor/designee in accordance with applicable timelines and will be required to file copies of all reports and related correspondence in the Investigator Site File.

For studies covered by the European Directive 2001/20/EC, the Sponsor's responsibilities regarding the reporting of SAEs/SUSARs/safety issues will be carried out in accordance with that Directive and with the related Detailed Guidance documents.

#### **7.4.1.6 Monitoring of Subjects with Adverse Events**

Any AE that occurs during the course of a clinical study and is considered to be possibly related to the IMP must be monitored and followed up by the Investigator until stabilization or until the outcome is known, unless the subject is documented as "lost to follow-up". Reasonable attempts to obtain this information must be made and documented. It is also the responsibility of the Investigator to ensure that appropriate additional therapeutic measures and follow-up procedures are performed if possible. The Sponsor or designee will actively follow-up and collect information on any AE that occurs during the course of a clinical study; however while this activity will continue for any SAEs until stabilization or until the outcome is known, it will be discontinued at the time of database lock for nonserious AEs.

#### **7.4.2 Pregnancy and In Utero Drug Exposure**

Only pregnancies considered by the Investigator to be related to study treatment (e.g., resulting from a drug interaction with a contraceptive medication) are considered to be AEs. However, all pregnancies with an estimated conception date during the period defined in Section 7.4.1.3 must be recorded by convention in the AE page/section of the eCRF. The same rule applies to pregnancies in female subjects and to pregnancies in female partners of male subjects. The Investigator must notify the Sponsor/designee in an expedited manner of any pregnancy using the Pregnancy Report Form, which must be transmitted according to the same process as described for SAE reporting in Section 7.4.1.4.

If possible, Investigators must actively follow-up, document and report on the outcome of all these pregnancies, even if the subjects are withdrawn from the study (see Section 5.5.2). The Pregnancy Report Form will be used to report outcomes and in case of adverse outcomes, the AE Safety Report Form (Clinical Trials) will be used for events occurring to the subject and the Parent Child/Fetus AE Report Form will be used if the child/fetus sustains an AE.

Adverse outcomes must be reported in an expedited manner as described in Section 7.4.1.4, while nonadverse outcomes must be reported within 45 days from delivery. In the event of pregnancy in a subject occurring during the course of the study, the subject must be discontinued from study medication immediately. The Sponsor must be notified without delay and the subject should be followed as described above.

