**Planned trial and treatment duration per subject**

Total duration of subject participation is approximately 420 days (60 weeks), which includes:

- Screening: 28 days (up to four weeks)
- DBPC Treatment: 364 days (52 weeks)
- Safety Follow-Up: 28 days (four weeks)

The optional LTE Treatment Period is approximately 104 weeks in duration and will be offered to subjects after completion of the DBPC Period.

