### 3.1 Benefit and Risk

No identified risks or new potential risks have emerged from clinical studies thus far. In the first in human Study EMR200527-001, M2951 was well tolerated. CCI [REDACTED]  
[REDACTED] In the completed Phase Ib study in subjects with SLE (Study EMR200527-002) M2951 was well tolerated. There were no SAEs reported during the study and no new safety signals were identified. Evidence of clinical benefit was not expected in this 4-week safety study. CCI [REDACTED]  
[REDACTED]

Important potential risks to subjects are based on nonclinical safety data of M2951 and clinical data on adverse drug effects associated with compounds of a similar pharmacological class. They include infection, leukopenia, thrombocytopenia, hemorrhage, gastrointestinal intolerance, renal toxicity, hepatocellular injury, atrial fibrillation, drug-drug interactions, and embryo-fetal toxicity. Asymptomatic elevations in amylase and/or lipase have been observed in completed clinical studies of M2951. The clinical significance and risk status of these observations are being assessed. The Sponsor is also assessing the clinical significance of convulsions observed in dogs at very high levels of exposure.

Risk minimization measures inherent to early phase clinical trials are considered adequate for the proposed clinical trial in subjects with SLE. An IDMC will continually review available safety and tolerability data and will be mandated to make immediate decisions regarding the conduct of the trial; no additional risk minimization measures are proposed. During the LTE, an internal SMC may review safety data on a regular basis during the LTE in lieu of the IDMC.

CCI [REDACTED]

CCI [REDACTED]

CCI

Taking the above information into account, benefit-risk considerations support conduct of the proposed clinical trial MS200527-0018 in subjects with SLE.

CCI

CCI

Refer to the Investigator's Brochure for more details of each study. This clinical trial will be conducted in compliance with the CTP, ICH GCP, and any additional applicable regulatory requirements.

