### 5.3.1 Inclusion Criteria

For inclusion in the study, all of the following inclusion criteria must be fulfilled:

1. Signed written informed consent before any study-related procedure is undertaken that is not part of the standard subject management and able to comply with requirements of protocol. In Japan, if a subject is < 20 years of age, the written informed consent from the subject's parent or guardian will be required in addition to the subject's written consent.
2. Male or female subjects, 18 to 75 years of age.
3. Diagnosis of SLE with either the SLICC criteria for SLE (see [Appendix II](#)), or at least four of the 11 ACR classification criteria for SLE (see [Appendix III](#)), of at least six months duration prior to Screening.
4. SLEDAI-2K total score  $\geq 6$  (including SLEDAI-2K clinical score  $\geq 4$ ) at Screening Visit.
5. Positive test results for anti-dsDNA antibody and/or anti-nuclear antibody (human epithelial cell-2 ANA  $\geq 1:80$ ) and/or anti-Smith (anti-Sm) antibody at the time of Screening.
6. Due to newly available nonclinical data, previous requirements for male participant contraception have been removed (see Section [6.5.3](#)).
7. A female participant is eligible to participate if she is not pregnant (see [Appendix I](#)), not breastfeeding, and at least one of the following conditions applies:
  - a. Not a woman of childbearing potential (WOCBP) as defined in [Appendix I](#)OR
  - b. A WOCBP who agrees to use 2 methods of birth control: a barrier method together with a highly effective method (i.e., methods with a failure rate of less than 1% per year) as detailed in [Appendix I](#) of this protocol for at least 28 days before start of first dose of study treatment (as appropriate), during the treatment period and for at least 90 days after the last dose of study treatment.
8. History of vaccinations, as per local guidelines:

- a. Vaccination against *Streptococcus pneumoniae* with PPSV23 and/or PCV13 or local equivalent with repeat administration as necessary to be up to date. If vaccination during Screening, there must be at least 2 weeks between vaccination and randomization.

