### 7.1.4 Safety Follow-Up/End of Study Visit

The Safety Follow-Up/End of Study Visit is scheduled four weeks (+ 5 days) after the last administration of study treatment. For subjects who do not participate in the LTE Period, the Safety Follow-Up Visit is scheduled four weeks (+ 5 days) after the last administration of study treatment in the DBPC Period. For subjects who participate in the LTE Period, the Safety Follow-Up Visit is delayed until four weeks (+ 5 days) after the last administration of study treatment in the LTE Period. Subjects who are approved to rollover into LTE Period after they entered, or completed, the DBPC Safety Follow-Up Period, may have two Safety Follow-Up Visits. Additional details of the Safety Follow-Up/ End of Study Visit are provided in the SOA.

Subjects who discontinue the IMP or withdraw from the trial early will attend the Safety Follow-Up Visit according to procedures described in [Sections 5.5.1 or 5.5.2](#), respectively.

All SAEs ongoing at the Safety Follow-Up/End of Study Visit must be monitored and followed up by the Investigator until stabilization or until the outcome is known, unless the subject is documented as “lost to follow-up”.

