
a. Typical use failure rates may differ from those when used consistently and correctly. Use should be consistent with local regulations regarding the use of contraceptive methods for participants participating in clinical studies.
 
b. Hormonal contraception may be susceptible to interaction with the study drug, which may reduce the efficacy of the contraceptive method. In this case, two highly effective methods of contraception should be utilized during the treatment period and for at least 90 days after the last dose of study treatment
 
c. Not approved in Japan.
 
d. For Japan only – the only approved barrier method is male condom with spermicide.

---

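### Mandatory pregnancy recording stops about four weeks after the last dose, while the protocol requires contraception for at least 90 days

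*Protocol*

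**What the plan says.** Section 7.4.2 counts a pregnancy as an AE only if the investigator considers it related to study treatment. By convention, however, it requires an AE-page entry in the eCRF for "all pregnancies with an estimated conception date during the period defined in Section 7.4.1.3". The same rule covers female subjects and female partners of male subjects. The section then asks the investigator to notify the sponsor of pregnancies on the Pregnancy Report Form and to follow their outcomes.

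Section 7.4.1.3 starts the period at the first signature of informed consent and carries it through post-treatment follow-up, "defined as the Safety Follow-Up Period (EOT through Follow-Up Week 4"). Section 7.1.4 says that the closing visit "is scheduled four weeks (+ 5 days) after the last administration of study treatment".

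Inclusion criterion 7b (Section 5.3.1) requires women of childbearing potential to use two methods of birth control "during the treatment period and for at least 90 days after the last dose of study treatment". Footnote b of the contraceptive guidance in Appendix I repeats the 90 days where hormonal contraception may interact with the study drug: two highly effective methods "should be utilized during the treatment period and for at least 90 days after the last dose of study treatment".

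Section 3.1 includes "drug-drug interactions, and embryo-fetal toxicity" among the important potential risks. Tables 1 and 2 place the last pregnancy test at the four-week Safety Follow-Up visit (Week 56, or LTE Week 108), and neither schedules any later contact.

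**The concern.** The protocol applies two post-dose horizons to one risk. For the participant, the precaution lasts at least 90 days. For the site, the duty to record a conception ends at about four weeks. A woman who conceives on day 45 is still within the period in which she agreed to use contraception. Yet the eCRF rule does not require her pregnancy to be recorded, and no planned visit, test or call would bring it to light.

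What is at stake is the completeness of the pregnancy data for a risk that the protocol itself names. If late adverse outcomes reach the sponsor through the open-ended rule for related SAEs, while late pregnancies with normal outcomes do not, the adverse reports cannot be set against the number of pregnancies they came from. An analysis plan cannot repair this later, because sites were never asked for the data.

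**Working it through.** The check is date arithmetic on the protocol's own figures, followed by one illustrative estimate.

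**Inputs**
- End of the recording window: Follow-Up Week 4 (Section 7.4.1.3).
- Length of Safety Follow-Up: the synopsis gives "Safety Follow-Up: 28 days (four weeks").
- Visit window: +5 days (Section 7.1.4; Tables 1 and 2).
- Contraception after the last dose: at least 90 days (criterion 7b; Appendix I, footnote b).

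**Reproducing the stated follow-up length.** In Table 1, Week 52 is Day 365 and Week 56 is Day 393: 393 − 365 = 28 days, which agrees with the synopsis. In Table 2, LTE Week 104 is Day 745 and Week 108 is Day 774: 774 − 745 = 29 days, which lies inside the 28-to-33-day range used below.

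**Recording window after the last dose.** Shortest 28 days; longest 28 + 5 = 33 days.

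**Part of the 90 days outside it.**
- Visit at day 28: 90 − 28 = 62 days; 62/90 = 68.9%.
- Visit at day 33: 90 − 33 = 57 days; 57/90 = 63.3%.

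Because 90 days is a minimum, these are the smallest gaps that the text allows.

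**How many pregnancies this might touch.** The protocol gives neither the number of women of childbearing potential nor a pregnancy rate, so both are assumptions: 200 to 400 women and 1% per year. The 1% sits at the upper bound of the failure rate that criterion 7b states for a highly effective method (below 1% per year).

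Expected number = women × annual rate × gap/365.
- 200 × 0.01 × 62/365 = 0.34
- 400 × 0.01 × 62/365 = 0.68
- With the 57-day gap: 200 × 0.01 × 57/365 = 0.31 and 400 × 0.01 × 57/365 = 0.62

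The range is about 0.3 to 0.7 pregnancies over the whole trial. It counts women who received only placebo, and it counts every conception in the gap, whether or not the site hears of it by another route.

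**With the windows aligned.** If recording for female subjects ran to the end of the contraception period, the uncovered part would be 0 days, and the window would be 57 to 62 days longer than now.

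**The case against.** The strongest reply is that other provisions already catch late pregnancies. The notification sentence in Section 7.4.2 has no time limit of its own. Section 7.4.1.3 keeps related SAEs reportable without limit, and Section 7.4.1.1 makes a congenital anomaly or birth defect an SAE. So a late pregnancy that the site learns of can reach the sponsor, and a birth defect judged related must. A reader might infer from the recording rule alone that these pregnancies simply go uncounted; the documents do not support that.

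What stands of the reply is partial. The notification sentence follows directly on the windowed rule, and the duty to follow outcomes refers back to the pregnancies just described, so its scope can be read either way. The SAE route omits normal outcomes and anomalies judged unrelated. Above all, detection after Week 4 is passive.

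A second reply is that the two windows serve different purposes: one is a precaution for the participant, the other a data-entry rule for the site. That is right. A reader might call them contradictory, but a site can comply with both.

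A third reply is that a conception after day 28 may involve no exposure. A reader might treat every conception up to day 90 as exposed. The legible text gives no half-life or washout for M2951, and the dose justification is redacted, so this cannot be settled here; the 90 days may include a safety margin. The case for alignment rests only on the protocol's own choice of 90 days.

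**Conclusion.** The misalignment is real. For women of childbearing potential, 57 to 62 of the 90 days after the last dose (63% to 69%) lie outside mandatory eCRF recording, and pregnancies conceived then are not actively ascertained. The first part follows from the stated windows and the second from the assessment schedules; neither needs an outside assumption.

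The practical yield is small: about 0.3 to 0.7 pregnancies under the assumed 200 to 400 women and 1% per year. Women treated only with placebo and late pregnancies reported by other routes would lower it. A higher rate would raise it: 3% with 400 women gives 400 × 0.03 × 62/365 = 2.0. Nothing in the protocol supports so high a rate, although Appendix I notes that failure rates in typical use may differ.

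The point does not apply to partners of male subjects, since Section 6.5.3 sets no contraception requirement for men.

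Because safety endpoints are primary in this trial, a reader might also infer that a primary endpoint is compromised. The documents do not support that. Section 8.3.1 does not list pregnancy counts, and Section 7.4.2 treats only treatment-related pregnancies as AEs. This is a cheap improvement in safety data capture and leaves the efficacy and safety analyses described in the protocol unchanged.

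**What to change.** In Section 7.4.2:
- keep the start of the window at informed consent. Starting at first dose would drop conceptions between consent and first dose, which are recorded now;
- for female subjects, extend pregnancy recording and outcome follow-up to the end of the post-dose contraception period already stated in Section 5.3.1;
- keep the existing window for partners of male subjects, who have no contraception period to refer to;
- state that the notification duty covers the same period, so that recording, notification and follow-up share one scope.

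Add a cross-reference in Section 7.4.1.3. Optionally, schedule one phone contact at the end of the contraception period for women of childbearing potential, so that detection no longer depends on the site happening to hear. If the sponsor prefers to leave the windows different, the protocol should give the reason.

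The cost is a short text change, a reporting period longer by 57 to 62 days for female subjects, and, if adopted, one call per woman. No contraception or treatment rule changes.
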